# C. Study Design and Research Methods

## Study Design:

This study will be a prospective non-randomized cohort study with patients presenting to Children's Hospital Colorado for resection of a central nervous system tumor. Due to heterogeneity of the pediatric central nervous system tumors and the evidence available, we will have a planned initial cohort (first phase) that will include tumor pathology that will allow us to test the feasibility of the study and the preliminary activity of fluorescein in the pediatric population. After completion of this initial cohort, we will expand our study to include tumors that are more specific to the pediatric population.

Currently, there exist many tumor types where there is robust literature on the use of fluorescein [3,4,6-15,21-26,27-29]. We plan to enroll patients based on a phased system and after completion of the first phase, we will perform a safety analysis as outlined below.

[name]: 18-0242 Page 3 Version: 07/03/2019

After safety analysis is completed, we will either proceed to the next phase, or in the event there is a safety concern, the DSMC will terminate our study. Terms for termination are detailed below.

Enrollment of ten patients is planned for each tumor type in each of the phases. The phases are designed to assess patients where evidence is available and proceed to tumor types where pediatric evidence is limited and the tumors are more unique to the pediatric population. This will allow us to safely assess patients and allow us to expand our trial in a controlled fashion. After completion of each phase of enrollment, we will continue enrolling the prior phase patients for a maximal total of 10 patients per each pathology group. Thus, maximal enrollment will be 20 patients for the first phase pathologies and 30 patients for the second phase pathologies, for a total enrollment of 50 treated patients and 150 historical controls

# First Phase of Study:

- High Grade Glioma
- Pilocytic Astrocytoma

# Second Phase of Study:

- Medulloblastoma
- Ependymoma
- Contrast Enhancing Spinal Tumors

# Study Drugs and Devices:

This study will employ the use of sodium fluorescein and an FDA approved operative microscope equipped with excitation and barrier filters for monitoring with sufficient fluorescent enhancement and contrast. Fluorescein sodium is a small organic salt with a molecular weight of 376 and excitation maximum at 494 nm and emission maximum at 521 nm. When injected intravenously, sodium fluorescein has a urine clearance of 24-72 hours. This agent accumulates in areas of diminished blood-brain barrier integrity and allows for determination of the margins between tumor and normal brain parenchyma [13].

#### Schedule of Events:

Table 1: Schedule of Events	Preop Assessment		ery and patient Stay	Outpatient Follow-Up
Visit Type (Standard of Care)	Neurosurgery Visit/Consult/H&P	Day of Surgery	Prior to Discharge	 Follow-Up Visit(s) Discharge through Month 2
Informed Consent/Assent	X			
Eligibility Assessment	X			
△Demographics	X			
△Medical History	X			
△Neurologic Exam	X		X	X
△Medical Exam	X		X	X
△Imaging (MRI/CT) of the brain and/or Spine	Х		Х	X
Δ Serum Creatinine	X			
△Pregnancy Test	X			
Sodium Fluorescein Administration		Х		

[name]: 18-0242 Page 4 Version: 07/03/2019

△Tumor Resection Surgery	X		
△Intraoperative	X		
Photography/Videography			
△Tumor Biopsy/Pathology	X		
Adverse Events	X	X	Χ

<sup>ΔStandard of care procedures, data will be collected via chart review.

#### Research Methods:

Study Recruitment: The primary neurosurgeons who will perform the resections will be investigators on the study and will identify eligible patients from their established practice. At the time surgical intervention is recommended, they will inform patients and parents/guardians of the existence of the study. Only those subjects with a clinical relationship with the study investigators will be recruited.

Informed Consent and Assent: Patients (and parents/guardians of child patients) will be informed of the risks and possible benefits of the study, and informed consent will be obtained before any research procedures are initiated. Those who are interested in participating in the study will be informed of the study details by a member of the research team. Ample time will be provided to answer any questions and concerns regarding the study during the consenting process and patients will be given the option to take the consent form home to review. Additionally, patients will be provided with contact information in the event that questions should arise. Patients who undergo emergent surgery in which there is not sufficient time to obtain informed consent will be excluded from the study. In children 7-17 years, informed assent will also be obtained. Patients 18 years and older will consent for themselves.

Eligibility Assessment: All inclusion/exclusion factors that result from procedures (imaging or laboratory tests) will already be clinically documented as part of the standard of care, so will be evaluated via chart review for the study. There are no study-specific screening tests or screening procedures.

The exclusion criteria "preoperative serum creatinine level > normal range and GFR < 30" will be evaluated through chart review (creatinine level is included in standard of care preoperative lab results). The reference ranges used by Children's Hospital Colorado's clinical lab will be used to determine the normal range based on the patient's age and gender. If a patient's serum creatinine is greater than the normal range, GFR will be calculated using the following equation. If the GFR is < 30, the patient will be excluded.

Table 2: GFR Calculation

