# III. Preliminary Studies/Progress Report:

To date, there are no published data using sodium fluorescein for the resection of central nervous system (CNS) tumors in children. Our group has considerable experience with the use of sodium fluorescein in adult tumors [19-20].

The neurosurgeons at Children's Hospital Colorado have extensive experience with pediatric brain and spine tumor surgery. They perform approximately 100 tumor surgeries each year, making them one of the busiest groups in the country. Their relevant research experience is formidable, having published 25 research articles related to brain and spine tumors in the last two years alone. Two of these papers were specifically about the use of sodium fluorescein in guiding adult brain tumor resections.

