Given this, we propose a 3:1 ratio of historical controls to fluorescein treated patients to match tumor location and histology. 150 historical controls will be pulled from the last ten years of Children's Hospital patients and matched to the 50 fluorescein treated cases on lesion location and pathology. This 3:1 ratio will strengthen our ability to objectively assess for adverse events related to sodium fluorescein as well as our extent of tumor resection analysis. Importantly, historical controls undergo stereotactic-guided tumor resection in a similar fashion to patients undergoing fluorescein administrations as outlined in our protocol.

All patients who undergo sodium fluorescein-aided resection will also have neuropathological analysis. We will analyze correlation of fluorescein staining to histopathology. Tissue obtained during the time of surgery will be used to correlate fluorescein staining to histopathological diagnosis. This data will be used to calculate sensitivity and specificity of fluorescein staining for tumors. Pre- and post-operative imaging will be used to assess the degree of the extent of resection in intraparenchymal tumors. Data collected from post-operative follow-up will be used to assess for potential complications/adverse reactions associated with sodium fluorescein administration.

For data analysis, extent of tumor resection will be compared as a continuous value across groups using a parametric ANOVA. Further calculations, such as sensitivity, specificity and positive predictive value will be calculated by contingency tables. Additionally, since group membership is not random we will run an adjusted analysis predicting the likelihood of tumor resection as a continuous outcome adjusting for demographic and co-morbidity factors. Significance will be assigned at p < 0.05.

Furthermore, adverse reactions and population/demographic data will be characterized using relative risk and odds ratios. Overall survival and progression free survival analysis will be characterized using Kaplan-Meier curves and compared across groups using a log rank test.

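### Treated patients are filtered by time for consent and by operating surgeon, but the control pull, the matching and the adjusted analysis state no counterpart

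*Combined protocol and SAP*

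**What the plan says.** Two rules in section IV.C (Research Methods) shape the treated group.

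- **Time for consent.** The paragraph on informed consent and assent says: "Patients who undergo emergent surgery in which there is not sufficient time to obtain informed consent will be excluded from the study." The rule removes only emergent cases that leave no time for consent. Urgent cases with time for consent stay in.
- **Operator.** The recruitment paragraph says: "The primary neurosurgeons who will perform the resections will be investigators on the study and will identify eligible patients from their established practice." It adds: "Only those subjects with a clinical relationship with the study investigators will be recruited."

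The controls are described in section IV.F (Data Analysis Plan): "150 historical controls will be pulled from the last ten years of Children's Hospital patients." They are matched to the treated cases on the site of the lesion and its pathology. On technique, the plan says that "historical controls undergo stereotactic-guided tumor resection in a similar fashion to patients undergoing fluorescein administrations as outlined in our protocol." Because the groups are not randomized, the plan adds an "adjusted analysis predicting the likelihood of tumor resection as a continuous outcome adjusting for demographic and co-morbidity factors." Neither surgeon nor urgency is named as a matching variable or as a covariate.

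**The concern.** With no randomization, the choice of controls and the adjusted analysis are the main protection against confounding. Two rules that decide who can enter the treated group have no stated counterpart for the controls.

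Both could bear on the primary outcome, extent of resection. Under Tumor Resection in section IV.C, the operation continues until the operating surgeon judges the goal met, so the outcome depends partly on who operates. An emergent operation may have a more limited goal. The same controls also serve the planned relative risks and odds ratios for adverse reactions, where urgency is a plausible confounder. If the control group contains cases of a kind that the treated group cannot contain, part of any difference between the groups may reflect case mix or operator instead of fluorescein.

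**Working it through.** **1. The two groups side by side**

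| Feature | Treated (IV.C) | Controls (IV.F) |
|---|---|---|
| Emergent, no time for consent | Excluded | Not addressed |
| Operator | Investigator neurosurgeons | Not addressed |
| Source | Investigators' own patients | Ten years of hospital patients |
| Lesion site, pathology | Defines the groups | Matched |
| Demographics, comorbidity | Adjusted | Adjusted |

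The eligibility list in section IV.B has no operator criterion. It does have a consent criterion, but patients found by chart review go through no consent step. Applying that list to controls would therefore not restrict the operator, and would deal with urgency only if the consent criterion were turned into a chart-based rule.

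**2. The plan's own sample-size figures**

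Inputs from section IV.F: means of 93.1% and 77.1% (difference 16 points), SD 25 points, alpha 0.05, taken as two-sided with equal groups. The normal approximation is n per group = 2 × (z for alpha + z for power)² × (25/16)². At 80% power this is 2 × (1.960 + 0.842)² × 2.441 = 38.3, so 39 per group and 78 in total. The t-test or ANOVA version, rounded up per group, gives 64, 80 and 106 at 70%, 80% and 90% power, which is exactly Table 3. The SD of 25 is therefore a fair basis for what follows.

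**3. Standard error for the planned 50 against 150**

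SE = 25 × √(1/50 + 1/150) = 4.08 points. The two-sided critical difference is 1.96 × 4.08 = 8.0 points. Power for 16 points is about 97%.

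**4. Illustration of bias**

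The documents give neither input here, so both are assumptions. Let q be the share of controls that the treated-group rules would have kept out, and d the amount by which their mean extent of resection is lower. The bias is b = q × d. With no true effect, the rejection rate is 1 − Φ(1.96 − b/SE) + Φ(−1.96 − b/SE).

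| q | d (points) | b (points) | b as share of 16 | Type I error |
|---|---|---|---|---|
| 5% | 5 | 0.25 | 2% | 0.050 |
| 10% | 10 | 1.0 | 6% | 0.057 |
| 20% | 10 | 2.0 | 13% | 0.078 |
| 30% | 10 | 3.0 | 19% | 0.114 |
| 20% | 20 | 4.0 | 25% | 0.165 |
| 30% | 20 | 6.0 | 38% | 0.312 |

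If such controls did better instead, the bias would run against fluorescein. A 3-point bias in that direction would reduce power for a true 16-point effect from about 97% to Φ((16 − 3)/4.08 − 1.96) = Φ(1.22), about 89%.

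These figures use the unadjusted comparison and ignore any gain in precision from matching.

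**The case against.** The case against has several parts, and some of it stands.

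- **Silence is not inclusion.** A reader might infer that the controls do contain emergency resections and other surgeons' cases. The documents do not support that. They only fail to exclude such cases. A reader might also take the treated group to be free of all emergent surgery, which it is not.
- **The consent criterion overlaps with the urgency rule.** The inclusion list requires a parent, guardian or adult patient able to go through consent, and a family with no time cannot. Section IV.C also counts the controls in total enrollment, so a reading in which the study criteria cover them is not ruled out. This stands in part, but a consent criterion cannot be applied directly to a past chart, so a retrospective definition is still needed.
- **The investigators may be the whole surgical group.** Section III describes the hospital's surgeons collectively: "The neurosurgeons at Children's Hospital Colorado have extensive experience with pediatric brain and spine tumor surgery." If they are all investigators, and if the same people operated throughout the ten years, the operator rule excludes no one. The documents state neither.
- **Technique is said to be similar.** That is partial mitigation, and it concerns method, not urgency or operator. It is also less reassuring for the spinal group, since section II says that neuronavigation is not available for spinal tumors.
- **The limitation is acknowledged.** Sections IV.E and IV.F recognize the lack of randomization, IV.E calls the study a pilot, and IV.F plans an adjusted analysis. That analysis does not name the two variables at issue.
- **The size is assumed.** This stands in full. Every value of q and d is illustrative, and the upper rows of the table need a large share of affected controls and a large difference together.

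**Conclusion.** The point holds as a gap in the control-selection and adjustment rules. As written, the plan does not stop controls from including emergent resections without time for consent or operations by surgeons who treat no study patient, and neither the matching nor the named covariates would correct for them.

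It does not hold as a demonstrated bias. The number of affected controls, and the size and direction of any effect, cannot be determined from the documents. Under the assumptions shown, the consequence runs from negligible (type I error 0.057 at a 1-point bias) to material (about 0.11 at 3 points). The 0.31 at 6 points is a pessimistic extreme. The comparison has ample power for 16 points, but power does not protect against bias of this kind. The change is worth making because it is inexpensive, not because the harm is known to be large.

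**What to change.** 1. In section IV.F, exclude from the control pull emergent operations that left no time for consent. Fix one chart-based definition before the charts are pulled, for example a stated minimum interval between the surgical decision and the operation. It must keep urgent cases with time for consent, as the treated group does. Excluding all emergent cases would make the controls stricter than the treated group.
2. Prefer controls operated on by the surgeons who also operate on treated patients.
3. Include operating surgeon as a factor in the adjusted extent-of-resection analysis. This complements step 2 and does not replace it: with a fixed surgeon factor, a surgeon who has only controls adds almost nothing to the treatment contrast.
4. If a tumor group then has too few controls (30 per group at 3:1 for ten treated patients), keep the others and report the result with and without them.

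The cost is protocol wording, two extra chart items and a somewhat smaller control pool in rare groups. It is an assumption, not something the documents state, that the operating surgeon and the timing of the operation can be read from the charts. If the investigators prove to be the whole surgical group for the full ten years, the surgeon preference costs nothing.

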# Serum Creatinine Reference Range

Age	Normal Range
31 to 364 Days	0.14 to 0.52 mg/dL
1 to 10 Years	0.23 to 0.61 mg/dL
11 to 17 Years	0.42 to 0.90 mg/dL
Female: 18 to 21 Years	0.52 to 0.99 mg/dL
Male: 18 to 21 Years	0.71 to 1.18 mg/dL

#### Calculation for GFR

$$\mathit{GFR} = \frac{0.41*\mathit{Height\ in\ cm}}{\mathit{Serum\ Creatinine\ in\ mg/dL}}$$

The exclusion criteria "pregnant or nursing mother" will be evaluated for females of childbearing potential. We will utilize Children's Hospital Colorado's perioperative definition of childbearing potential as females who have reached menarche or are 12 years of age or older. Pregnancy testing is standard of care for these patients and pregnancy test results will be evaluated through chart review.

[name]: 18-0242 Page 5 Version: 07/03/2019

<sup>1See Follow Up section below for more detail

Pre-operative Evaluation: A standard of care neurosurgical assessment will occur at admission: standard clinical evaluation for tumor including pertinent history, physical and neurologic exam data, laboratory findings, and initial imaging studies will all be documented clinically and recorded via chart review for the study.

Imaging: Patients will have pre- and post-operative imaging in accordance with the standard clinical procedures at Children's Hospital Colorado. Patients in this study will not require any study-specific imaging outside the standard of care. All post-operative images are reviewed by fellowship trained pediatric specific neuroradiologists. Neuroradiologists are not informed on the administration of sodium fluorescein and will conduct review of the post-operative imaging per standard protocol. No imaging evidence of sodium fluorescein is visible on post-operative MR or CT imaging and the independent neuroradiologist is blinded to the operative course of the patient.

Sodium Fluorescein Administration: Patients enrolled in this study will receive 3 mg/kg sodium fluorescein following induction of anesthesia by administration into a peripheral venous line over 10 seconds. This dose has been previously reported for use in a pediatric population and has been studied in adult tumor population [15]. Previous studies have used doses ranging from 500mg standing to 20mg/kg with minimal side effects [7]. The FDA-approved dosage for children is 7.7 mg/kg intravenously. A lower dose and earlier administration reduces the incidence of fluorescent contamination of normal brain. Furthermore, the advent of new neurosurgical microscopes with fluorescein filters decreases the dosage required to observe fluorescence.

Tumor Resection: Resection of the lesions will proceed as normal as if sodium fluorescein had never been given. Resection will proceed with the use of a surgical microscope equipped with excitation and barrier filters for monitoring with sufficient fluorescent enhancement and contrast. The surgeon will be capable of switching the filters so as to observe the ordinary microscopic image and the fluorescein image as necessary. This ensures that the safety and normal operating procedure are minimally disturbed during this study.

Fluorescein absorbs at a peak between 465-490 nm which is selected for from the light source by the excitation filter. The barrier filter will only permit fluorescence emitted by sodium fluorescein in the 500-530 nm range to the surgeon's eye. The margins of resection will be based on identifying the fluorescein stained tissue that indicates neoplastic change and breakdown of the blood brain barrier. The resection will be performed piece by piece until the primary surgeon feels that surgical goal is achieved. Samples of fluorescent tissue will be sent to pathology for evaluation of histology.

Utilizing the microscope's internal recording device, we will record or photograph the surgery. When possible, biopsy location will be marked on the patient's preoperative MRI with the neurosurgical navigation device and a screenshot of this localization will be taken from the device system. This will only be possible for intracranial lesion and will not be used for spinal lesions. Images will be stored on a password-protected encrypted computer on the Children's Hospital Colorado server and accessible only to the investigators. Biopsies will be sent to pathology for diagnosis as is customary in all tumor resections, and diagnosis will be followed up in the patient's medical record by authorized study personnel. Fluorescein staining will be correlated with biopsies/pathological samples based on samples collected per standard of care. Official pathology reports will be used to determine pathological correlations with fluorescein staining.

Follow-Up: A neurosurgical assessment will occur post-operatively prior to discharge, as well as at standard of care outpatient follow-up clinic visits that take place between discharge and Month 2 post-surgery. These clinic visits typically occur at one week (for incision check) and one month post- surgery. Standard clinical evaluation for tumor includes pertinent history,

[name]: 18-0242 Page 6 Version: 07/03/2019

physical, neurologic exam data, and may also include laboratory findings and post-operative imaging studies. These will all be documented clinically and recorded via chart review for the study. Patients will be followed for the study through Month 2 (or 8 weeks) post-surgery.

Furthermore, any adverse events occurring after surgery will be collected until 7 (for non-serious AEs) or 30 days (for SAEs) after the last day of study intervention (administration of fluorescein). All adverse events will be followed for outcome information until resolution or through Month 6 post-surgery.

For example, if a patient has no adverse events following surgery, they will only be followed through end of study period which is 2 months post-surgery. If the patient had adverse events within the first 30 days, those adverse events will be followed through resolution or 6 months post procedure, whichever comes first.

Re-Enrollment: Patients who have previously been enrolled in this study and received prior administration of fluorescein sodium as a part of this study for guided tumor resection are eligible for re-enrollment into the study, should further surgical resection be clinically indicated. Patients will receive the same dosage as outlined in the protocol of 3mg/kg. Clearance of 500mg of fluorescein sodium is 24-72 hours after administration of a single dose [16]. Patients re-enrolled into the study will be eligible after 3 days given the clearance time necessary for fluorescein sodium. Patients will be enrolled with the same study number. Patients will be reconsented at time of re-enrollment.

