#### IV. Research Methods

### A. Outcome Measure(s):

The primary outcome measure will be extent of tumor resection. For all patients, pre-operative imaging and post-operative imaging will be used to analyze the extent of resection of the tumors. In intracranial lesions, the use of volumetric imaging tools will be used to calculate the extent of tumor resection. In spinal lesions, manual measurement will be used to determine the extent of resection.

Secondary outcome measures include the subjective utility of fluorescein per the operating surgeon, as well as positive predictive value, sensitivity and specificity for extent of tumor resection. Additional outcome measure(s) will vary depending on the neurosurgical tumor removed. Intraoperative videos and images will be collected from the surgical case. Images obtained will be correlated to tissue biopsy and will aid in the analysis of fluorescein

[name]: 18-0242 Page 2 Version: 07/03/2019

extravasation in pediatric neurosurgical tumors. All tissue samples collected will be taken for histopathological analysis.

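### Sensitivity and specificity of fluorescein staining are planned, but neither non-fluorescent specimens nor a staining status per specimen is required, so neither measure is assured to be unbiased

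*Combined protocol and SAP*

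**What the plan says.** Section A (Outcome Measures) lists among the secondary outcomes "positive predictive value, sensitivity and specificity for extent of tumor resection". Section F describes a measure of staining against histology: "Tissue obtained during the time of surgery will be used to correlate fluorescein staining to histopathological diagnosis", followed by "This data will be used to calculate sensitivity and specificity of fluorescein staining for tumors". The method is given in one sentence: "Further calculations, such as sensitivity, specificity and positive predictive value will be calculated by contingency tables".

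On sampling, the Tumor Resection paragraph of section IV.C says "Samples of fluorescent tissue will be sent to pathology for evaluation of histology". The same part of IV.C says that staining will be compared with specimens taken in routine care, and that pathology reports are the reference. Section A adds "All tissue samples collected will be taken for histopathological analysis".

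On linking stain to specimen, section IV.C says "we will record or photograph the surgery", and section A says "Images obtained will be correlated to tissue biopsy".

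On how the stain influences surgery, the Tumor Resection paragraph makes two statements. One has the resection carried out just as it would be without the dye. The other sets the resection margins by the stained tissue.

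**The concern.** A two-by-two table of staining against histology has four cells. Two of them, non-fluorescent tumour and non-fluorescent normal tissue, can be filled only by specimens that did not fluoresce. The plan names a source for the fluorescent row and leaves the other row to whatever routine sampling yields. It sets no number, site or selection rule for non-fluorescent specimens. It does not define what counts as fluorescent, does not require a status for each specimen, and does not mention selective verification.

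If the chance that tissue reaches pathology depends on whether it fluoresced, the observed sensitivity and specificity reflect the sampling as well as the dye. A sensitivity close to 100% that comes from sampling alone could be read as evidence that the stain finds tumour reliably in children. The low specificity that would go with it would be just as uninformative.

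**Working it through.** **Figures in the plan.** The documents give no specimen numbers, no sampling rates, and no assumed sensitivity, specificity or precision. There is therefore no stated figure to reproduce. Table 3 in section F concerns extent of resection and has no bearing here.

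**Inputs, all assumed.** Se and Sp are the true sensitivity and specificity. f is the rate at which non-fluorescent tissue is sampled, relative to fluorescent tissue of the same kind (tumour or normal). f = 1 means that sampling does not depend on fluorescence.

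**Formulas.**

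- Apparent sensitivity = Se / (Se + (1 − Se) × f)
- Apparent specificity = Sp × f / (Sp × f + (1 − Sp))

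**Illustration with Se = 0.80 and Sp = 0.90.**

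| f | Apparent sensitivity | Apparent specificity |
|---|---|---|
| 1 | 0.80 / (0.80 + 0.20) = 80.0% | 0.90 / (0.90 + 0.10) = 90.0% |
| 0.50 | 0.80 / (0.80 + 0.10) = 88.9% | 0.45 / (0.45 + 0.10) = 81.8% |
| 0.25 | 0.80 / (0.80 + 0.05) = 94.1% | 0.225 / (0.225 + 0.10) = 69.2% |
| 0.10 | 0.80 / (0.80 + 0.02) = 97.6% | 0.09 / (0.09 + 0.10) = 47.4% |
| 0 | 0.80 / 0.80 = 100% | 0 / 0.10 = 0% |

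At f = 0, specificity is 0/0, hence undefined, if no fluorescent specimen turns out to be normal tissue.

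**Dependence on the assumed true values, at f = 0.10.**

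- Se = 0.70, Sp = 0.80: sensitivity 0.70 / 0.73 = 95.9%; specificity 0.08 / 0.28 = 28.6%.
- Se = 0.90, Sp = 0.95: sensitivity 0.90 / 0.91 = 98.9%; specificity 0.095 / 0.145 = 65.5%.

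The direction is the same in each case; the size changes with the inputs.

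**Positive predictive value.** With an assumed tumour share of 0.70 among candidate sites, and fluorescent tumour and fluorescent normal tissue sampled at the same rate, PPV = 0.70 × 0.80 / (0.70 × 0.80 + 0.30 × 0.10) = 0.56 / 0.59 = 94.9%. f does not appear, so under-sampling of non-fluorescent tissue leaves PPV alone. It is not immune to selection, though. If fluorescent normal tissue is sampled at half the rate of fluorescent tumour, PPV becomes 0.56 / (0.56 + 0.015) = 97.4%.

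**Is f below 1 plausible here?** The margin statement in the Tumor Resection paragraph points that way: tissue beyond a stain-defined margin is less likely to be removed and sent. The neighbouring statement, that surgery is unaffected by the dye, points to f near 1. The text does not settle the matter.

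**The case against.** The strongest reply is that the plan does not confine histology to fluorescent tissue. All collected samples go to pathology, routine sampling may include unstained pieces, and images are to be compared with biopsies. This stands in part. A reader might infer that no non-fluorescent specimen will exist, or that specificity cannot be calculated at all; the documents do not support that. But incidental specimens do not make sampling independent of fluorescence, and comparing images with biopsies is not a recorded call on each specimen.

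A second reply is that every number above is assumed. That is correct. The figures show what the design permits, not what this trial will see.

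A third is that PPV is no safer, because the choice of fluorescent samples is also unspecified. This stands to the extent shown in the working: PPV avoids the missing row of the table but still depends on which fluorescent tissue is taken.

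A fourth concerns section A. It is tempting to treat its reference to extent of resection as a slip for the staining measure in section F. The documents do not establish this. Extent of resection is judged on imaging, so section A could mean a separate imaging-based measure, which the specimen argument would not reach.

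Finally, a yes/no field is of little use without a definition of positive and a link to the matching pathology result. That is right, and the fix includes both.

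**Conclusion.** The concern holds in this form: sensitivity and specificity of staining are committed to, while the sampling and recording they need are not required, so neither is assured to be unbiased. If non-fluorescent tissue is under-sampled, sensitivity is overstated and specificity understated. With true values assumed at 80% and 90%, the result would be 94% and 69% at a quarter of the fluorescent sampling rate, and 98% and 47% at a tenth. With no such specimens, the values are fixed by construction. The actual size cannot be derived from the documents, and the direction rests on under-sampling, which the margin statement makes plausible but does not prove.

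A reader might go further and infer that the trial's main result is compromised. It is not: these are secondary outcomes, and the primary outcome and the sample size calculation do not depend on them.

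**What to change.** 1. For every specimen already sent to pathology, record fluorescent yes or no at removal and before histology, using a stated definition of positive, and link the entry to that specimen's pathology result.
2. Report PPV per specimen with a confidence interval clustered by patient. Re-enrolled patients keep their study number (Re-Enrollment paragraph, section IV.C) and should count as one cluster. State that PPV applies only to the fluorescent tissue actually sampled.
3. Report non-fluorescent specimens as counts with their histology. Label any sensitivity or specificity as descriptive, conditional on the specimens sampled and subject to verification bias, and do not use it as an estimate of staining accuracy.
4. State whether the accuracy measures in section A are the staining-versus-histology measures of section F or a separate imaging-based measure, and make the two sections agree.
5. Reconcile the two statements in the Tumor Resection paragraph on how fluorescence affects the resection. No clinical rule is proposed here.

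The cost is a wording change and one data field per specimen, with its definition and link. No extra biopsy is needed. The downside is that two secondary outcomes become descriptive.
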